1.1 Disease Background

1.1.1 Scope of Problem

Malignant Fibrous Histiocytoma/ Undifferentiated Pleomorphic Sarcoma (MFH/UPS) represents a group of soft tissue sarcoma (STSs) considered to be of probable fibrohistiocytic or fibroblastic lineage. UPSs account for 10% of adult STSs and represent one of the most common STSs of older adults, with most occurring in patients between the ages of 50 and 70 years [1]. Pediatric UPSs are rare. The etiology is unknown, although some of these tumors occur in a previously irradiated field. The most frequent location are the limbs followed by the trunk. As for other STSs, surgery performed by an experienced surgeon plus radiotherapy remain the cornerstone of treatment of nonmetastatic tumors. With the majority of these tumors being high grade, perioperative chemotherapy is an option, but recurrence/metastasis is common. In the metastatic setting, doxorubicin as a single agent is considered the standard first choice (ORR<20%), but is also used in combination with ifosfamide (ORR 26%), which assumes that the findings with these treatments in other STSs also are applicable to UPS [2]. In fact, despite being one the most common STS subtypes, few data are available in this specific subtype. Other drugs such as gemcitabine and docetaxel, and pazopanib also have shown activity in the advanced setting. Median survival in advanced STS ranges from 12-20 months on average [3,4]. Patients with advanced UPS have the worst outcome compared with other histologic STS subtypes [5]. Metastatic/recurrent high-grade myxofibrosarcoma has a similar behaviour to UPS. Some pathologists might call high grade myxofibrosarcoma with pleomorphic cells as UPS. **No standard of care or FDA approved agents specific to this subtype exist. There is an urgent unmet and critical need to develop novel agents for this orphan disease.**

1.1.2 Rationale for use of Immunotherapy in UPS

Compared to “immunogenic” tumors such as melanoma characterized by high mutation rates, STS are considered to be immunologically “quiet.” [6] Among STS subtypes, however, some histologies such as undifferentiated pleomorphic sarcoma (UPS) are characterized by complex genomic features, and a baseline immune infiltrate, which may provide immunologic mutated protein targets, and may respond to immune checkpoint inhibition [7]. T-cell infiltration and PD-L1 expression were found to be higher in sarcomas with complex genomics and particularly in UPS than in other STSs. Indeed, this was described in the recently reported open-label phase II

SARC028 trial (NCT02301039) of anti-PD-1 monotherapy in patients with advanced bone and soft tissue sarcomas [8]. In the SARC028 study, pembrolizumab demonstrated promising activity in UPS with a 40% overall response rate in the first 10 patients, with median PFS of 7 months (95% CI: 1.9-15.9). This study was expanded to include a total of 40 UPS patients, and though the ORR reported was lower at 23% with a median PFS of 3 months, among the included subtypes, UPS was still the subtype with the highest activity [9]. Activity of checkpoint inhibitors in this subtype was also seen in the Sarcoma Alliance study with nivolumab plus ipilimumab with ORR of 18% (2/11) [10]. In these studies high-grade myxofibrosarcoma patients were also included.

Based on this information, we propose a phase II clinical trial evaluating the efficacy and safety of sintilimab in subjects with UPS/ high-grade myxofibrosarcoma to explore activity of Sintilimab in UPS.

Study Hypothesis: Sintilimab, fully humanized anti-PD1 antibody, can result in durable tumor responses in advanced refractory UPS.

1.2 Investigational Drug (Sintilimab)

1.2.1 Mechanism of action

Immune checkpoints are a type of immune inhibitory molecule, whose physiological function is to regulate the intensity and extent of the immune response and to avoid damage and destruction of normal tissues. Cancer cells often manipulate these immune checkpoints to escape immune surveillance. The efficacy of drugs designed to block the actions of immune checkpoints such as, CTLA-4 and PD-1/PD-L1, has been validated clinically.

PD-1, the receptor primarily expressed on activated T-cells, has two ligands, PD-L1 and PD-L2. PD-L1 is the main ligand that is expressed on activated T-cells, antigen-presenting cells, and tumor cells [11]. The binding of PD-1 with PD-L1 plays an important role in regulating T cell activation and maintaining peripheral immune tolerance. When T cells do not express PD-1, they interact with antigen-presenting cells to enable the activation and proliferation of T cells as well as the secretion of activated cytokines, which can kill tumor cells. Activated T cells begin to express PD-1. After PD-1 binds to the ligand PD-L1 expressed on the surface of antigen-presenting cells or tumor cells, the inhibitory signal transmitted by PD-1 inhibits the proliferation of T cells and the secretion of activated cytokines, thus weakening the function of T cells. Most tumor cells evade the attack from immune cells through this mechanism. The activity of T cells

and their ability to kill cancer cells can be restored by blocking the PD-1/PD-L1 interaction with drugs [12].

Sintilimab is a recombinant fully human IgG4 anti-PD-1 monoclonal antibody (R&D code: IBI308). Multiple preclinical in vitro and in vivo studies have demonstrated the ability of sintilimab to block the PD-1 pathway. The anti-tumor activity of murine analogs of sintilimab has also been demonstrated in various murine tumor models.

1.2.2 Clinical study results of sintilimab

A Phase 1a dose-escalation trial was initiated in Sep. 2016 to evaluate 4 dose levels (1 mg/kg, 3 mg/kg, 200 mg, and 10 mg/kg) of sintilimab. The Phase 1a trial has enrolled 9 subjects (3 for each arm) in 3 treatment arms (1 mg/kg, 3 mg/kg, and 200 mg), and evaluated the dose-limiting toxicities specified in the protocol for each arm. No dose-limiting toxicities were observed.

The preliminary pharmacokinetic (PK) results of sintilimab in subjects with multiple tumors demonstrated a typical IgG4 PK with a slow elimination ($t_{1/2} \approx 17.3$ d). The elimination half-life is similar to the physiological half-life of IgG4.

The pharmacodynamic (PD) results showed that: a dose of sintilimab at 1 mg/kg rapidly (24 h) saturated peripheral PD-1 ($95.8 \pm 2.3\%$) and maintained the receptor occupancy with decreasing concentrations throughout the study. The minimum concentration at steady state was 13 $\mu\text{g/mL}$ and peripheral PD-1 receptor occupancy was maintained.

Following completion of the dose escalation trial, clinical studies of sintilimab for the treatment of lymphomas and solid tumors were subsequently conducted. A total of 595 Chinese subjects and 36 US subjects received ≥ 1 dose of sintilimab, of which 534 Chinese subjects and 36 US subjects received sintilimab monotherapy, and 61 Chinese subjects received sintilimab in combination with chemotherapy. Over 93% of the subjects completed at least 2 cycles of treatment, 83.5% completed at least 3 cycles of treatment, 73.6% completed at least 4 cycles of treatment, and 65.9% completed at least 5 cycles of treatment. The median treatment duration for subjects that received 200mg Q3W was 24.29 weeks (range: 9.57~57.86 weeks).

Overall, a total of 77.3% of Chinese subjects (460/595) experienced a sintilimab-related adverse events (TRAE), the three most common ($\geq 10\%$) TRAE including fever (15.0%), hypothyroidism (14.1%), and increased AST (13.6%). A total of 18.7% (111/595) of subjects had TRAE \geq grade 3, among which the most common (incidence $\geq 1\%$) were decreased platelet count (1.2%), decreased neutrophil count (1.0%), and decreased lymphocyte count (1.0%). A total of 55.6% of

US subjects (20/36) experienced sintilimab-related adverse events (TRAЕ), the most common (\geq 10%) included fatigue (16.7%), nausea (13.9%), and diarrhea (13.9%).

A total of 29.4% of Chinese subjects (175/595 subjects) experienced treatment-emergent SAEs during the study. The most common treatment-emergent SAEs included lung infection (4.0%), pneumonia (2.5%), and pulmonitis (2.5%). A total of 36.1% of US subjects (13/36 subjects) experienced treatment-emergent SAEs during the study. The most common treatment-emergent SAEs included urinary tract infection (8.3%), pleural effusion (5.6%), and hypotension (5.6%). The overall safety profile of sintilimab is comparable with current globally marketed PD-1/PD-L1 products.

In US, one Phase 1b study (IND #136159) is ongoing that enrolls patients with solid tumors, and a Phase 3 trial in patients with first line esophageal squamous cell carcinoma (IND #145675) has also been initiated.

1.3 Risk/Benefit Assessment

1.3.1 Potential risks

Considering the mechanism of action and the clinical safety information available for IBI308, the additional adverse events (AEs) in the sintilimab arm that occur during this clinical trial are expected to be the immune-mediated inflammatory response resulting from the activation of immune system, e.g. pneumonitis, colitis, hepatitis, renal insufficiency, and endocrine events. According to the available clinical data, anti-PD-1 monoclonal antibodies are well-tolerable despite a high incidence of adverse reactions. Treatment discontinuation due to adverse reactions only occurs in a small number of subjects, and most events resolve after appropriate interventions. As early symptoms of immune-related adverse events (irAEs) vary, the investigators should pay extra attention to early signs and symptoms of irAEs during the trial, make decisions promptly, adjust the dose according to Section 5.2 in the protocol, and provide effective treatment measures to reduce the subject's risk.

1.3.2 Potential benefits

Pharmacological and safety data from multiple clinical trials showed that sintilimab has clear pharmacological activity and good tolerability in subjects with advanced cancers. Similar drugs have shown significant anti-tumor activity in subjects with advanced UPS, supporting the conduct of clinical trials in subjects with advanced UPS.

2 Study Objectives

2.1 Primary Objectives

- To evaluate the efficacy of sintilimab in subjects with UPS (ORR at 12W by RECIST 1.1)

2.2 Secondary Objectives

- To evaluate the ORR (RECIST 1.1) and DCR, PFS, OS, safety and DOR of sintilimab in subjects with UPS

2.3 Exploratory Objectives:

- To evaluate the correlation between biomarkers in tumor tissue and efficacy, including but not restricted to PD-L1 expression level, tertiary lymphoid structures (TLS) transcriptome sequencing, single-cell sequencing, and multicolor immunohistochemistry (IHC) analyses
- To evaluate the correlation between biomarkers in peripheral blood and efficacy, including but not restricted to soluble PD-L1, circulating tumor DNA (ctDNA), identification/quantification of immunologic changes, and cytokine analyses.

[figure not shown]
3 Study Design

3.1 Overall Design

This is a Phase 2 clinical trial evaluating the efficacy and safety of sintilimab in subjects with UPS. Subjects with unresectable, locally advanced, recurrent or metastatic UPS will be enrolled. A total of 25 evaluable subjects will be enrolled and treated. Subjects will be treated with sintilimab (200 mg IV on Day 1 Q3W). The treatment will be repeated every 3 weeks until progressive disease (PD), intolerable toxicity, initiation of new anti-tumor therapy, withdrawal of informed consent, lost to follow-up, completion of therapy, death, or any other investigator-determined reasons for treatment discontinuation (whichever occurs first). Treatment will be infused for a maximum period of up to 24 months (starting from the first dose). During the trial, tumor imaging evaluation will be initially performed once Q6W (\pm 7 days) and Q9W (\pm 7 days) starting from Cycle 7, and will be based on RECIST 1.1, until PD (assessed at 12W or after), initiation of new anti-tumor therapy, withdrawal of informed consent, lost to follow-up, death, or completion of the study (whichever comes first). After the completion or discontinuation of the

study treatment, safety follow-up (30 days \pm 7 days and 90 days \pm 7 days after the last dose) and survival follow-up (every 60 days \pm 7 days) will be performed. The primary endpoints of the trial will be confirmed ORR per RECIST v.1.1.

Figure 1 Schematic of SiARa-UPS study design and administration

3.2 Definition of Study Completion

The subject is considered to have completed the study if the survival follow-up is completed or the subject withdraws consent.

The trial is completed if the last subject has completed the survival follow-up, been treated for 24 months, or the sponsor decides to discontinue the trial early and/or the agreement between sponsor and health authority.

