4.4.2 Subject withdrawal

A subject has the right to withdraw from the study at any time for any reasons. A subject must withdraw from the study if the subject or his/her legal representative withdraws informed consent.

A subject can withdraw from the study for the following:

- Screen failures;
- A subject or his/her legal representative withdraws informed consent;
- Death;
- Lost to follow-up;
- Study completion.

A subject who withdraws from the study will no longer receive the treatment and protocol-specified follow-up visits. However, the investigator should make every effort to persuade him / her to complete all the examinations specified for the end-of-treatment visit.

The reasons for withdrawal should be documented in the electronic case report forms (database). A subject who has signed the ICF and received any study interventions cannot be replaced after withdrawal or treatment discontinuation.

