4.4.3 Lost to follow-up

A subject is considered lost to follow-up when he/she fails to return to the study site for 2 consecutive scheduled visits and the site personnel are unable to contact the subject.

The following actions must be taken if a subject does not return to the study site for a scheduled visit:

- The study site should try to contact the subject, reschedule the missed visits, reiterate the importance of complying with the schedule of visits, and confirm whether he/she is willing and/or should continue to participate in the study.
- Before a subject is considered lost to follow-up, the investigator or designee should make every effort to recontact the subject (at least 2 phone calls should be made; if the subject

is still out of contact, a letter should be mailed to the subject's last known address). These attempts to contact the subject should be documented in the subject's medical records or study documents.

The subject is considered lost to follow-up and determined to have withdrawn from the study if the subject is still unable to be contacted.

5 Study Drugs and Other Treatments

The study drug is sintilimab. The first dose of study treatment would be designated Day 1 of Cycle 1. For the rest of the treatment cycles, the study treatment can be administered 3 days before or 3 days after the scheduled day of administration. Treatment can be delayed for up to 1 week if the administration day is on a holiday or if the subject is otherwise unavailable.

Table 3 Dosage and administration

Study Drug	Dose	Frequency	Route	Treatment Cycle
Sintilimab	200 mg	Q3W	IV infusion	on Day 1, every 21 days

The study drugs in **Table 3** is provided by the drug/supporting company. The administering institution (MD Anderson Cancer Center) is responsible for recording the batch numbers, manufacturers, and expiration dates.

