6.2.6 Survival follow-up

After completing the safety follow-ups, the subject should be contacted (telephone visits are allowed) once every 60 days (\pm 7 days) to obtain the survival information, any subsequent systemic anti-tumor therapy, and PD information. Long-term follow-up should be continued until death or 3 years after last patient enrolled.

Subsequent anti-tumor therapy

The investigator or qualified designee will collect all the information about new anti-tumor therapies initiated after the last dose of the study drugs and the corresponding efficacy. If the subject initiates a new anti-tumor therapy within 30 days after the last dose, then the safety follow-up must be performed before initiation of the new therapy.

The subject should be followed for survival after initiation of a new anti-tumor therapy. Refer to Section [6.2.6](#) – Survival follow-up for details regarding survival follow-up.

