9.3.1.2 Design and sample size/power

The primary efficacy endpoint will be confirmed ORR at 12W. A patient will be considered as a responder to the treatment if he/she has achieved confirmed complete response (CR) or partial response (PR) determined by RECIST 1.1.

A Simon's two-stage Minimax design will be used to monitor the efficacy of sintilimab. The null hypothesis involves an ORR of 10% that will be tested against an ORR of 30%, i.e. a 20% improvement. In the first stage, 15 patients will be treated. If there is ≤ 1 patient who achieves objective response in these 15 patients, the study will be terminated. If the study moves forward to second stage, an additional 10 patients will be treated leading to a total of 25 patients. Six or more responders out of the 25 treated patients will be considered clinically relevant to justify further investigation. The power of this design is 80% under the 1-sided type I error rate of 5%. The early stopping probability is 55% if the ORR is 10% and the average sample size would be 19.5. Assuming a 5% dropout rate, we will need to enroll up to a total of 27 patients.

Analysis of key and other secondary efficacy endpoints

The key secondary efficacy endpoints are ORR (RECIST 1.1), DCR, DOR, PFS and OS in the evaluable and ITT populations.

The ORR, DCR and corresponding exact 95% CIs of the sintilimab arm will be estimated using binomial distribution.

PFS is the time from first dose to first date of Investigator-determined progression (by imaging),

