9.3.3 Compliance

The frequency and proportion of subjects who violate the treatment regimen will be presented.

The proportion of subjects administered study drugs of doses between 80–110% of the dose specified in the protocol, who complete the study in accordance with study protocol, and who complete different number of treatment cycles will also be summarized.

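### Section 3.2 defines withdrawal of consent as study completion, against 4.4.2; applied to the completion proportion in 9.3.3, it would overstate that descriptive figure.

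*Combined protocol and SAP*

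**What the plan says.** Section 3.2 (Definition of Study Completion) gives two routes to completion for a subject: "The subject is considered to have completed the study if the survival follow-up is completed or the subject withdraws consent".

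Section 4.4.2 (Subject withdrawal) puts the same event under a different disposition: "A subject must withdraw from the study if the subject or his/her legal representative withdraws informed consent". It adds the consequence: "A subject who withdraws from the study will no longer receive the treatment and protocol-specified follow-up visits". Its list of reasons for leaving the study has withdrawn consent, death, loss to follow-up and study completion as separate items. It also requires the reason for withdrawal to be recorded in the database.

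Section 4.4.3 handles loss to follow-up: "The subject is considered lost to follow-up and determined to have withdrawn from the study if the subject is still unable to be contacted". Section 6.2.6 sets the length of survival follow-up: "Long-term follow-up should be continued until death or 3 years after last patient enrolled".

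Section 9.3.3 (Compliance) promises a summary of the proportion of subjects "who complete the study in accordance with study protocol, and who complete different number of treatment cycles will also be summarized". It neither defines completion nor refers to 3.2, and it names no denominator.

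On dropout, section 9.3.1.2 says: "Assuming a 5% dropout rate, we will need to enroll up to a total of 27 patients".

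**The concern.** A completion figure tells the reader how many subjects were followed as planned. Under 3.2 a subject who leaves early by withdrawing consent has the same status as one followed to the end. A subject who leaves in the same week by being lost to follow-up does not, although the missing data are the same.

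The rest of the protocol treats the two states as different. Besides 4.4.2, sections 3.1 and 7.1.2 list withdrawal of consent and completion of the study as separate reasons for imaging to end.

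What is at stake is one descriptive proportion. In a trial of about 25 patients, one or two misclassified subjects visibly change it. It is also one of the figures a reader would use to judge how much follow-up was cut short. Two programmers working from the same data could report different values, each able to point to protocol text.

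**Working it through.** **Inputs.** Target of 25 patients, 5% dropout and 27 enrolled (9.3.1.2); completion rule (3.2); consent withdrawal as study withdrawal (4.4.2); loss to follow-up as withdrawal (4.4.3). The documents give no number of consent withdrawals, so w is assumed and varied.

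**The plan's own figures.** 25 / 0.95 = 26.3, rounded up to 27, as stated. The allowance is therefore 27 − 25 = 2 patients. The two-stage design also reproduces:

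- At a response rate of 10%, the probability of stopping early is 0.9^15 + 15 × 0.1 × 0.9^14 = 0.549 (stated 55%).
- The expected sample size is 15 + (1 − 0.549) × 10 = 19.51 (stated 19.5).
- The exact two-stage binomial calculation gives power 0.802 at 30% (stated 80%) and type I error 0.033 at 10%, within the 5% limit.

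None of these figures uses the completion definition.

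**How each type of subject is classified.**

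| Subject | Under 3.2 | Under 4.4.2 / 4.4.3 |
|---|---|---|
| Followed to death | Completer (follow-up ends at death, 6.2.6) | On the withdrawal list, as death |
| Withdraws consent at week 5, no restaging scan | Completer | Withdrawn |
| Lost to follow-up at week 5, no restaging scan | Not a completer | Withdrawn |

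The second and third rows carry the same loss of information and are classified oppositely by 3.2. The first row shows a second overlap, caused by the list in 4.4.2.

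**Size.** Let w be consent withdrawals and k be subjects whose survival follow-up is incomplete for any other reason, such as loss to follow-up.

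- Rule in 3.2: (N − k) / N
- Consent withdrawals not counted as completers: (N − w − k) / N
- Difference: w / N, whatever the value of k

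With k = 0:

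| N | w | Rule in 3.2 | Withdrawals excluded | Difference (points) |
|---|---|---|---|---|
| 25 | 1 | 100% | 96.0% | 4.0 |
| 25 | 2 | 100% | 92.0% | 8.0 |
| 25 | 5 | 100% | 80.0% | 20.0 |
| 27 | 1 | 100% | 96.3% | 3.7 |
| 27 | 2 | 100% | 92.6% | 7.4 |
| 27 | 5 | 100% | 81.5% | 18.5 |

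The row with N = 27 and w = 2 uses the plan's own allowance and supposes that both dropouts withdraw consent. The levels of 100% and 92.6% also need everyone else to finish survival follow-up. The 7.4-point gap does not: with k = 1 the figures are 26/27 = 96.3% and 24/27 = 88.9%.

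**The case against.** The strongest reply concerns the link between the sections. Section 9.3.3 sits under a compliance heading, does not cite 3.2, and qualifies completion by adherence to the protocol. Read as a compliance measure, it would not count someone who left at week 5. Section 3.2 may also have been meant only to say when participation ends. This stands in part: the documents do not show that the overstated figure will be reported, only that it follows if 3.2 is applied as written. It does not remove the defect, because the compliance reading is written nowhere and 3.2 is the only definition available.

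A reader might infer that all dropouts would count as completers. They would not; loss to follow-up is not completion under 3.2.

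A reader might also infer that withdrawals would be hidden, or that the dropout allowance could not be checked. The text does not support that either. Section 4.4.2 requires withdrawal reasons in the database, so the counts can be tabulated. The completion proportion by itself would not show them.

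Finally, the size is illustrative. The 5% allowance is not defined as consent withdrawal and is not tied to long-term survival follow-up.

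**Conclusion.** The contradiction between 3.2 and 4.4.2 is real, and it is a wrongly stated rule rather than a missing detail. Its effect is an overstatement of w/N in one descriptive proportion, about 4 points per consent withdrawal, conditional on 9.3.3 being computed with the 3.2 definition. The value of w and the denominator are assumptions.

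It would be tempting to conclude that the efficacy results are affected. They are not. The evaluable set for response (9.2, 9.3.1.1) depends on measurable disease and a restaging evaluation. The Simon rule counts responders. The censoring text for the time-to-event endpoints uses imaging and first-dose dates. Section 9.3.5 presents progression and death dates for all subjects. A subject who withdraws before the first scan is outside the evaluable set whatever disposition label is used. This is a low-cost correction worth making, not a threat to the primary conclusion.

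**What to change.** 1. **Section 3.2:** delete the consent-withdrawal clause. Define a subject as having completed the study when followed to death or to the end of the survival follow-up period in 6.2.6.
2. **Section 4.4.2:** remove both study completion and death from the list of withdrawal reasons. Removing only the first would leave a subject followed to death as both a completer and a withdrawal.
3. **Section 9.3.3:** cite the 3.2 definition for the completion proportion, and report consent withdrawals and losses to follow-up as separate counts. Stating the denominator at the same time would settle the choice between 25 and 27.

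The cost is wording edits in three sections, with no new data and no change to sample size or decision rule. The one downside is that the reported completion rate may be slightly less favourable.
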